### 3.0 Intervention to be studied.

**Study Overview.** In this open-label pilot, we will recruit 25 veterans with PTSD from the Ralph H. Johnson VAMC PTSD Clinical Team (PCT), as overseen by Col, licensed clinical psychologist, and Section Chief, [name]. Massed imaginal exposure will be delivered via VVC or any other VA approved telehealth platform, modeled after the in-person protocol of Zoellner et al., (2017). Following the initial assessment of PTSD and related symptoms and impairment, all veterans will receive six daily 60-minute telehealth sessions focusing on imaginal exposure therapy (details below). The initial assessment will

be repeated at 1-week post-treatment and 1-month post-treatment completion. As an open-label, feasibility pilot study, there is no control arm.

**Intervention: VVC-delivered Massed Imaginal Exposure.** Consistent with Zoellner et al., (2017), six, 60- minute daily sessions of imaginal exposure will be conducted based on the PE manual (Foa et al., 2007). Session 1 will include rationale for imaginal exposure and common reactions to trauma. Sessions 2-6 will focus on imaginal exposure (45 minutes) and processing (15 minutes), with later sessions focused on the most distressing aspect of the trauma memory. The final session will include relapse prevention. Between-session assignments will include listening to audio recordings of sessions at least once. All sessions will be delivered within a 10-day window. If participants do not respond, they will be offered additional services at no additional cost or loss of benefits for which they would otherwise be entitled.

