## 1.0 Objectives / Specific Aims

The goal of this project is to establish the safety, feasibility, and acceptability of abbreviating and accelerating telehealth-delivered imaginal exposure therapy for post-traumatic stress disorder (PTSD). Importantly, conventional telehealth-delivered Prolonged Exposure (PE) therapy is non-inferior to the conventional, gold standard in-person PE for PTSD (Acierno et al., 2017). Intensive or massed schedules of in-person exposure- based trauma-focused treatments have likewise recently been shown, in a nascent but promising literature, to produce comparable treatment outcomes to conventional once or twice weekly schedules, but importantly, with lower levels of premature dropout (Sciarrino et al., 2020; Zoellner et al., 2017).

**AIM 1: Establish the safety of VVC-delivered massed imaginal exposure for PTSD.** We hypothesize that VVC-delivered, massed imaginal exposure will be safe as indexed by no significant adverse events.

**AIM 2: Establish the feasibility, tolerability, and acceptability of VVC-delivered massed imaginal exposure for PTSD.** We hypothesize that 1) veterans will consider the treatment acceptable and tolerable and that 2) recruitment and retention will be feasible (> 80% retention).

**EXPLORATORY AIM 1: Establish acceptability among stakeholder providers of VVC-delivered massed imaginal exposure for PTSD.** We hypothesize that 1) telemental healthcare providers will consider the treatment acceptable and tolerable and that 2) will be willing to receive training and/or refer patients to such services.

**EXPLORATORY AIM 2: Establish the preliminary efficacy of VVC-delivered massed imaginal exposure for PTSD.** We hypothesize that 1) veterans will demonstrate moderate reductions in posttraumatic stress and associated symptoms and impairment from intake to the end of treatment that will in turn, 2) be maintained or extended at the 1-month post-treatment follow-up.

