**Table 1. Eligibility Criteria**

Inclusion Criteria:
1. Age 18-65.
2. Ability to speak, read, and write English.
3. Diagnosis of PTSD based on CAPS-5 (> 3 mo. post-trauma).
4. Seeking treatment for PTSD at the Charleston VA.
5. Willingness and ability to engage in assessment and treatment visits through VVC, or another VA-approved telehealth videoconferencing platform.
Exclusion Criteria:
1. Currently receiving psychotherapy for another anxiety- or stress-related condition.
2. Current substance use disorder diagnosis with repeated abuse or dependence within 3 months of study entry and unwillingness to abstain for 24 hours prior to study visits.

---

3. Unstable dose of psychotropic medications within 6 weeks prior to baseline assessment (based on the DMSC; see measures).
4. Medical condition that would contraindicate participation in treatment or assessment activities (e.g., severe cardiovascular problems; based on MINI, DMSC, and chart review; see measures).
5. Current, or history of bipolar I disorder (based on MINI; see measures).
6. Current, or history of psychotic symptoms (based on MINI; see measures).
7. Serious suicidal risk or a suicide attempt in the past year, as determined by self-report (PHQ-9) and clinical interview (C-SSRS; see measures).
8. Active neurological conditions, e.g., seizures, stroke, loss of consciousness or concussion (based on MINI, DMSC, and chart review; see measures)

---

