## 10.0 Data Management

**Data Acquisition.** If (and only if) ultimately approved by the VA, we propose the use of VA Qualtrics, which is a secure, FedRAMP-authorized online data capture system that is widely used as a HIPPA-compliant web-based means to collect sensitive research data. Moreover, if approved, in addition to remotely collecting validated self-report questionnaire data from participants using this platform, we also request leveraging Qualtrics' functionality to integrate java script, which would enable us to directly capture audio and visual data from the participant's side from their webcam and microphone. This is an excellent alternative to our initially proposed procedures, which involve collecting streamed, then captured (i.e., on the clinician's side) footage. This is problematic due to significant temporal distortion and low sampling rate for screen-captured footage on currently deployed telehealth platforms approved by the VA (i.e., Teams, Webex, and VVC). As mentioned, the use of Qualtrics will be entirely contingent on obtaining full MUSC IRB and VA R&D approval for our proposed use. If ultimately not approved, we will continue to implement our procedures that involve capturing questionnaire data with hard copies, by mail.

**Data Preparation.** Pre-processing of data as the study progresses will allow for more expedient dissemination of study findings. As appropriate, pre-processing will follow standard best practices to ensure excellent data quality and security. Prior to analyses, data will be visually and statistically inspected for the presence of aberrant data points, which will be omitted prior to analyses.

**Analytical Plan.** Descriptive statistics will be reported for safety, feasibility, tolerability, and acceptability. Linear mixed-effects models will be used to characterize trajectories of change in symptoms and impairment, while controlling for potential confounders, such as baseline severity.

Following standard pre-processing steps, analyses will be conducted using generalized linear models, and will proceed in a bottom-up manner involving selection of the best fitting fixed and random growth terms, followed by adding predictors of interest. Factors (e.g., sex) will be dichotomously coded, whereas all continuous predictors will be scaled and centered as a function of baseline values to allow for meaningful interpretation of effects as indicative of reliable change.

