Additionally, all models will control for baseline levels of the outcome to control for individual differences at pre-treatment in estimating effects. Model refinement will be guided by theory, evaluating standard fit statistics (e.g. Log Likelihood, AIC, BIC, etc.) and whether modeling assumptions are sufficiently met.

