#### **14.0 Potential Benefits to Subjects or Others**

We believe that the potential risks to participants are minimal and are minimized further given the steps we will take to reduce and respond to participants' distress and to maintain confidentiality. Further, participants may benefit from receiving imaginal exposure, which is a core component of Prolonged Exposure (PE) therapy – a gold-standard evidence-based treatment for PTSD. However, while our group's prior work has suggested comparable efficacy of massed imaginal exposure relative to the full PE protocol (Zoellner et al., 2017; Sciarrino et al., 2020), it is unknown whether these effects will generalize to a telehealth modality, and thus these potential benefits cannot be guaranteed. Should participants fail to respond, additional treatment will be offered.

Benefits to others are potentially substantial. If successful, this pilot study may provide support for developing alternative treatment schedules to afford flexibility and accommodate preferences, reduce burden on patients, providers, and clinic resources, and provide support for more developing more efficacious, efficient, and accessible treatments for PTSD.

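### Further treatment offered to non-responders is neither dated nor recorded, so it could make gains look maintained at 1 month when the six sessions did not maintain them

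*Combined protocol and SAP*

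**What the plan says.** All participants receive six daily telehealth sessions. The baseline assessment is then to "be repeated at 1-week post-treatment and 1-month post-treatment completion" (Section 3.0), which leaves about three weeks between the two later visits.

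The offer of further care appears twice. Section 3.0: "If participants do not respond, they will be offered additional services at no additional cost or loss of benefits". Section 14.0: "Should participants fail to respond, additional treatment will be offered". Neither place defines response, names the visit at which it is judged, or gives the type or start date of the care.

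The hypothesis affected is the second part of Exploratory Aim 2 (Section 1.0), that symptom reductions will "be maintained or extended at the 1-month post-treatment follow-up". No margin, significance level or decision rule goes with it.

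The Analytical Plan in Section 10.0 states: "Linear mixed-effects models will be used to characterize trajectories of change in symptoms and impairment, while controlling for potential confounders, such as baseline severity". It adds that "all models will control for baseline levels of the outcome to control for individual differences at pre-treatment in estimating effects". It gives no estimand, no handling of scores after further treatment and no missing-data rule. Section 3.0 also says: "As an open-label, feasibility pilot study, there is no control arm".

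On recording, the assessment schedule in Section 9.0 has no post-treatment item on other treatment, and the demographics form is completed before treatment only. Chart review is named for attendance and compliance. The eligibility table lists as an exclusion "Currently receiving psychotherapy for another anxiety- or stress-related condition", but this applies at entry and does not govern follow-up.

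**The concern.** Further care is offered selectively, to the participants who are doing worst. If some of them start it before the 1-month visit and improve, the 1-month mean moves towards the hypothesis for a reason other than the durability of the six sessions. With no control arm, no comparison can separate the two.

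The circumstances make this plausible. The PCL-5 and PHQ-9 are completed before every session, and the full battery is repeated at 1 week, so poor response can be seen early. Participants are seeking PTSD treatment at the same VA, and Section 6.0 describes telehealth trauma-focused therapy as standard practice in its PTSD clinic.

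At stake is whether a finding of maintained gains can be read as a property of the intervention. The gap may also become permanent: Section 11.0 deletes the links between identifiers and research data at study completion, after which the charts could no longer be matched to the scores.

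**Working it through.** **1. The plan's own figure.** The only sample-size figure is the enrolment target in Section 4.0: 20 completers with a 20% allowance gives 20 / (1 - 0.20) = 25. It reproduces and is not affected by this point. There is no figure for the maintenance hypothesis to reproduce.

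**2. Shift in the 1-month mean.**

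Shift = (share not responding) x (share of those who start further care before the 1-month visit) x (improvement from that care by the visit, in SD of the score).

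Inputs:
- Share not responding: 25-60%. Section 2.0 gives about 25-50% non-remission and about 60% poor response. These are general background rates, not rates for this intervention.
- Uptake before the visit: 0%, 50% or 100%. Assumption.
- Effect: 0.3-0.5 SD. Assumption.

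| Uptake before 1 month | Low end | High end |
|---|---|---|
| 0% | 0 | 0 |
| 50% | 0.25 x 0.5 x 0.3 = 0.04 SD | 0.60 x 0.5 x 0.5 = 0.15 SD |
| 100% | 0.25 x 1 x 0.3 = 0.08 SD | 0.60 x 1 x 0.5 = 0.30 SD |

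**3. What a shift of this kind does to the reading.** A simulation used 20 completers, an assumed correlation of 0.7 between the 1-week and 1-month scores, the worst 1-week scorers as non-responders, 50% uptake and a 0.5 SD effect (the top of the assumed range). A two-sided paired t-test at 0.05 served as a yardstick; the plan names no such test. There were 20,000 runs per setting.

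| Setting | Shift | True 0.5 SD relapse detected | Significant further gain when nothing changed |
|---|---|---|---|
| No further care | 0 | 78% | 2.6% |
| 25% non-response | 0.06 SD | 62% | 4% |
| 50% non-response | 0.125 SD | 47% | 8% |

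**4. Comparison with sampling error.** With 20 completers, the 95% half-width for the mean 1-week to 1-month change is 2.093 x sqrt(2(1 - r)) / sqrt(20), in SD units. For an assumed r of 0.5 this is 2.093 x 1.00 / 4.47 = 0.47. For r of 0.8 it is 2.093 x 0.63 / 4.47 = 0.30. The illustrative shifts are at or below that.

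**5. Values a sensitivity analysis could set aside.** At full uptake, 25-60% of 20 is 5 to 12 one-month values. At 50% uptake it is 2.5 to 6.

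**The case against.** A reader might infer that the plan analyses the 1-month visit as though no further care was given, and that a bias is therefore built in. The documents do not support that. They do not say that any care starts before the 1-month visit, and the default use of all scores is inferred from silence. The direction is conditional too: the care must begin and help within about three weeks. Non-responders who left the study would instead create missing data, which the plan also leaves open.

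The size is equally uncertain. The non-response shares describe PTSD patients in general, while for massed treatment Section 2.0 cites large effects (d = 1.15-2.93) and low attrition, so the true share could be lower. The plan speaks of an offer, not of uptake. The shift is also no larger than the sampling error.

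The stakes are limited. Only the 1-month half of an exploratory aim is touched. Section 2.0 says the study is not powered for efficacy and that pre-to-post estimates are what will inform later trials. Safety, feasibility and acceptability are unaffected, and the 1-week estimate is affected only if care starts within that first week.

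Finally, using all observed scores is a legitimate treatment-policy estimand.

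Most of this stands. It makes the bias possible rather than established, and it argues against replacing the all-data estimate. It does not remove the gap. Sampling error is visible in the interval; a selective shift in one direction is not. Without dates, no reader could tell whether it occurred.

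**Conclusion.** The concern holds in conditional form. The plan offers further care to non-responders, does not say whether it may start before the 1-month visit, does not record it, and does not say how later scores are used. If such care starts before that visit and helps, the maintenance estimate can be biased in favour of its hypothesis.

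The size cannot be derived from the documents. The ranges of 0.04-0.15 SD at 50% uptake and 0.08-0.30 SD at full uptake rest on assumed uptake, an assumed 0.3-0.5 SD effect and borrowed background rates. The shift is zero if all such care starts after the 1-month visit.

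A reader might go further and want the estimate restricted to scores before further care to become the main one. The documents do not require that. It is a choice of estimand, and it could set aside 5 to 12 of 20 values, concentrated among the poorest responders, and then depend heavily on a missing-at-random assumption.

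The gap is still worth closing, because the repair is cheap and may not be possible once the identifier links are deleted.

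**What to change.** 1. Add to the planned CPRS chart review the type and start date of any further PTSD treatment between session 6 and the 1-month visit. Collect this before the identifier links are deleted.
2. Report how many participants received such treatment before the 1-month visit. If none did, the two estimates below coincide and the concern falls away.
3. Keep the all-data 1-month estimate, labelled as including any further treatment.
4. Pre-specify beside it a sensitivity estimate from the same mixed model, with scores after the start of further treatment set to missing. State its assumption: given the earlier scores in the model, the values set aside are missing at random. Keep the 1-week score, and the session scores where the measure has them, in the model, because they carry the information on non-response.
5. Conclude that gains from the six sessions were maintained only if both estimates agree. Say in advance what agreement means, since the plan sets no margin.

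The cost is one chart-review field, one extra model run and a sensitivity estimate that is less precise than the main one. Enrolment stays at 25. The offer of care and its timing are clinical matters and are left as they are.

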#### 4.0 Inclusion and Exclusion Criteria/ Study Population

Veterans who are aged 18-65 (inclusive), who meet full DSM-5 criteria for current PTSD will be recruited from all racial, ethnic and gender categories. The rationale regarding a cutoff of 65 years was for correspondence to prior massed in-person protocols (e.g., Zoellner et al, 2017). Planned follow up studies will include a broader age range and will be powered to analyze age effects on outcomes. To contend with dropout, we propose to enroll 25 veterans, with the aim of completing assessments and treatment for 20 participants. In-person investigations have shown a dropout rate of 5% (Sciarrino et al. 2020), thus a 20% allowance will ensure adequate recruitment to meet study aims.

**Exclusion Criteria.** Participants will be excluded for the following: 1. clinically unstable physical illness; 2. bipolar Type I disorder; 3. dementia; 4. repeated abuse or dependence upon drugs within 3 months; 5. unstable psychotropic regimen within 6-weeks; and finally, 6. active suicidal ideation or a suicide attempt within the past year.

**Table 1. Eligibility Criteria**

Inclusion Criteria:
1. Age 18-65.
2. Ability to speak, read, and write English.
3. Diagnosis of PTSD based on CAPS-5 (> 3 mo. post-trauma).
4. Seeking treatment for PTSD at the Charleston VA.
5. Willingness and ability to engage in assessment and treatment visits through VVC, or another VA-approved telehealth videoconferencing platform.
Exclusion Criteria:
1. Currently receiving psychotherapy for another anxiety- or stress-related condition.
2. Current substance use disorder diagnosis with repeated abuse or dependence within 3 months of study entry and unwillingness to abstain for 24 hours prior to study visits.

---

3. Unstable dose of psychotropic medications within 6 weeks prior to baseline assessment (based on the DMSC; see measures).
4. Medical condition that would contraindicate participation in treatment or assessment activities (e.g., severe cardiovascular problems; based on MINI, DMSC, and chart review; see measures).
5. Current, or history of bipolar I disorder (based on MINI; see measures).
6. Current, or history of psychotic symptoms (based on MINI; see measures).
7. Serious suicidal risk or a suicide attempt in the past year, as determined by self-report (PHQ-9) and clinical interview (C-SSRS; see measures).
8. Active neurological conditions, e.g., seizures, stroke, loss of consciousness or concussion (based on MINI, DMSC, and chart review; see measures)

---

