## 7.0 Recruitment Methods

As part of standard clinic procedures, all referrals receive a diagnostic assessment and are asked if they would like to hear about opportunities to participate in research. If Veterans respond that they are interested in being contacted about research opportunities and if they choose to begin evidence-based therapy (the modal treatment choice in the PCT), then study staff will make contact regarding potential enrollment prior to the Veteran's first therapy session. Communication between clinic and study staff will be facilitated by the PI. Research recruitment is well-integrated with the standard clinic operating procedures and similar recruitment strategies in this environment have supported successful recruitment goals of multiple studies in recent years. In support of a high likelihood of expeditious attainment of recruitment goals, in FY20, the PCT completed nearly 600 assessments for trauma-focused therapy, and triaged over 1500 consults for PTSD and related conditions via VVC. Further, the PCT has a longstanding history of supporting successful recruitment for numerous studies targeting treatment innovations.

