## 8.0 Consent Process

All participants will be referred on the basis of a routine intake assessment in the PCT or another VA behavioral health clinic prior to study entry. As indicated above in the eligibility criteria, those who report clinical symptoms that suggest trauma-focused therapy for PTSD is not in their best interests will be excluded from the study and directed to alternate care as recommended by the PCT and their clinical care team. Participants who appear to meet criteria for entry into the study will be informed of the study and if they express interest, they will review

study consent, and HIPAA Authorization with study personnel (PI, study coordinator, or study evaluator).

The consent process and HIPPA authorization procedures will be completed electronically through VVC or another VA-approved videoconferencing platform, following all VA institutional guidelines pertaining to the consent and authorization procedures. Consent documents will be provided by mail, or through secure messaging, then subsequently reviewed with study personnel at the first study visit (i.e., the pre-treatment or baseline assessment). During review of consent, study staff will detail study procedures and ensure that patients understand what components are part of the study procedures and what is part of standard treatment for PTSD. Study staff will ensure that potential participants understand the study and are interested and able to complete study procedures prior to providing signed informed consent. Participants will receive in the consent document emergency contact information for use in case of acute exacerbation of symptoms. Participants will be informed that they can withdraw from the study at any time and receive alternate care outside of the study. Participants will also be informed that if they report imminent suicidality or intolerance for study procedures at any point during the protocol, they may be withdrawn from the study and receive alternate care as appropriate (i.e., inpatient hospitalization, treatment in outpatient psychiatry, etc.).

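### Eligibility Table 1, Exclusion 1 does not cover current psychotherapy for PTSD itself, and no listed measure is described as recording it

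*Combined protocol and SAP*

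**What the plan says.** **Eligibility.** Exclusion 1 in Table 1 of section 4.0 reads "Currently receiving psychotherapy for another anxiety- or stress-related condition". Inclusion 3 requires a PTSD diagnosis on the CAPS-5, and Inclusion 4 is "Seeking treatment for PTSD at the Charleston VA". The prose list in the same section, which opens "Participants will be excluded for the following: 1. clinically unstable physical illness; 2. bipolar Type I disorder; 3. dementia", has six items and none of them concerns psychotherapy. For medication there is an explicit stability rule, Exclusion 3: "Unstable dose of psychotropic medications within 6 weeks prior to baseline assessment".

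**Route of entry.** Section 3.0 recruits from the PCT. Section 7.0 says that, for Veterans who are interested in research and opt for evidence-based therapy, "study staff will make contact regarding potential enrollment prior to the Veteran's first therapy session". Section 8.0 is wider: referral follows "a routine intake assessment in the PCT or another VA behavioral health clinic prior to study entry".

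**After treatment.** Sections 3.0 and 14.0 offer further services to participants who do not respond. Neither says when, relative to the 1-month assessment.

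**Data and analysis.** None of the measures in section 9.0 is described as recording psychotherapy received outside the study. The analytical plan in section 10.0 names baseline severity as its example of a confounder and does not mention other psychotherapy. Section 3.0 states that there is no control arm. Section 2.0 calls efficacy preliminary and unpowered, but says that the pre-post effect sizes and variances will help to plan follow-up randomised trials.

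**The concern.** The protocol guards against two co-interventions, unstable psychotropic medication and psychotherapy for neighbouring conditions. The one most likely to move the symptom scales, psychotherapy for PTSD, falls outside the wording. A participant who entered while in such therapy, or who began it before the 1-month visit, would contribute a change score that mixes two treatments. As the measures are described, the data would not show which participants these were.

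At stake are the Exploratory Aim 2 estimates: the change from intake to the end of treatment, and the hypothesis that gains hold or grow by 1 month. Being unpowered makes these estimates imprecise. It does not protect them from bias, and they are intended as inputs to the design of later trials.

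**Working it through.** **Step 1: does any criterion close the gap?**
- Exclusion 1: in a table whose inclusions concern PTSD, the word *another* means other than PTSD. Current PTSD therapy is not covered.
- Inclusion 4: a Veteran can seek PTSD treatment at this site while already receiving some elsewhere. It does not require that none is under way.
- Prose list in section 4.0: no psychotherapy item. It also omits the psychotic-symptom and neurological exclusions of Table 1, so it is an abbreviated list and its silence adds little.
- Section 7.0: contact before the first session protects the PCT route, but this describes when staff call, not who is eligible.
- Section 8.0: referral from another clinic is also based on a routine intake. That makes ongoing therapy there less likely but does not rule it out.
- Therapy outside the VA: nothing addresses it.

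No criterion closes the gap. The recruitment text narrows it.

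**Step 2: the plan's own figure.** Section 4.0 aims for 20 completers with a 20% allowance: 20 / (1 - 0.20) = 25. This matches the stated enrolment. It is not in dispute and supplies the denominators below.

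**Step 3: possible size.** The documents give no rate of concurrent PTSD therapy and no effect for it, so both inputs are assumptions. If k of 25 participants have it and it shifts the change in each by c SD, the mean shifts by (k/25) × c:
- k = 0: 0 for any c
- k = 2: c = -0.5 gives -0.04; c = +0.5 gives +0.04; c = +1.0 gives +0.08
- k = 5: c = -0.5 gives -0.10; c = +0.5 gives +0.10; c = +1.0 gives +0.20

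If only 20 complete and all five such participants are among them, the largest figure becomes (5/20) × 1.0 = 0.25.

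Negative values are included because a Veteran who still meets full PTSD criteria during therapy may have made the gains before baseline or may respond poorly.

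**Step 4: scale.** For an assumed standardised pre-post change d = 0.5 with n = 20, SE is approximately √(1/n + d²/(2n)) = √(0.05 + 0.00625) = 0.237. The 95% half-width is 1.96 × 0.237 = 0.46. The largest illustrative shift with 25 analysed, 0.20, is less than half of that.

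**Step 5: exposure time.** Treatment follows within 1 week of baseline, sessions fit in a 10-day window, and the first reassessment is 1 week later: at most about 7 + 10 + 7 = 24 days. A full 1.0 SD from parallel therapy in that time is an extreme assumption. Counting a month as 30 days, the 1-month visit falls at about 7 + 10 + 30 = 47 days, which leaves more room, including for services offered after non-response.

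**The case against.** The strongest reply is that the route of entry already does the work. Recruitment is from the PCT, contact precedes the first session, referral from either clinic follows an intake assessment, and participants must be treatment-seeking. The offers of further treatment after non-response, and of alternate care on withdrawal, suggest that the study treatment is meant to serve as the participant's PTSD therapy. This stands as a reason to expect few cases, perhaps none. It does not replace an eligibility rule, and it does not cover therapy outside the VA, earlier therapy in another VA clinic, or therapy begun during follow-up.

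It can also be said that section 9.0 may not describe every item collected. Exclusion 3 relies on the demographics and military service form for medication, which that form's description does not mention, and chart review is already planned. So the absence of a psychotherapy record is an inference from short descriptions. That is fair, and it is why the remedy asks for an explicit record.

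Four stronger readings are tempting, and the documents do not support them:
- A reader might infer that Exclusion 1 is what prevents symptom change from being attributed to the study treatment. With no control arm, time, regression to the mean and expectancy would remain under perfect wording, and the protocol presents efficacy as preliminary.
- A reader might infer that the bias must flatter the treatment. The direction is not established.
- A reader might infer that the safety aim is compromised. Aim 1 is indexed by the absence of significant adverse events and reported descriptively; that criterion does not require events to be allocated between therapies.
- A reader might infer that participants will start PCT therapy alongside the study. No rule forbids it, but the surrounding text points to substitution.

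**Conclusion.** The point holds as a defect of scope in a stated rule. Exclusion 1 as written does not exclude current PTSD psychotherapy, no other criterion does so, and no listed measure is described as capturing it. The remaining exposure is mainly therapy outside the PCT or the VA, plus therapy begun before the 1-month visit.

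The consequence is a possible bias in the exploratory pre-post and 1-month estimates, of unknown size and direction and possibly zero. The illustrative range of -0.10 to +0.20 SD rests wholly on assumed inputs (0 to 5 of 25 affected, -0.5 to +1.0 SD each) and is small beside sampling error at this sample size. It does not alter the sample size, and it bears little on the safety and feasibility aims. It is worth correcting because the estimates feed later trial planning and the correction is cheap.

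**What to change.** 1. Extend Exclusion 1 to current psychotherapy for PTSD as well as for another anxiety- or stress-related condition. Reconcile the prose list in section 4.0, the recruitment text in section 7.0 and the referral text in section 8.0 with it. If the sponsor means to allow concurrent PTSD therapy, say so instead; item 2 then matters more.
2. Record any non-study psychotherapy from baseline to the 1-month visit, with its target condition and start date. Use the CPRS review already planned for attendance, and add one question at the 1-week and 1-month visits to pick up care outside the VA.
3. Have the same record show whether further services offered to non-responders began before the 1-month assessment, since sections 3.0 and 14.0 leave that timing open.
4. Report the frequency beside the effect estimates. If there are any such participants, add a descriptive estimate without them, keeping therapy under way at baseline apart from therapy begun afterwards. Dropping people who sought more care because they had not responded would itself favour the treatment, so this estimate should accompany the main one and not replace it.

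The cost is a short amendment, one question at two existing visits, and a few otherwise eligible Veterans lost. Against 25 participants and nearly 600 PCT assessments in FY20 (section 7.0), that loss should be easy to absorb.
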